- **C4. Potential problems & alternative approaches for all Aims:** We hypothesize that HIIT will improve DSP outcomes. We also believe that the effect of HIIT will be greater than the effect of bariatric surgery. However, our supportive preliminary data are based on a diet-induced weight loss intervention, and the effect of surgical weight loss may be larger. If surgery is as good as or better than HIIT, the results would still lead us toward one of the first disease modifying therapies for DSP. Our study design is also able to look at the combined effects of HIIT and bariatric surgery. If the severity of DSP is less in our population, the IENFD of the proximal thigh may not be the most sensitive DSP outcomes measure; however, we plan to use IENFD of the distal leg as a secondary outcome measure. In contrast to our supportive preliminary data, if the HIIT regimen is difficult to perform for this obese population, we could switch interventions to a conventional exercise regimen, which [name] has extensive experience with in patients with obesity and diabetes.
- C5. Biorepository to enable future mechanistic studies: We will obtain fasting plasma DNA, urine, skin

biopsies, and subcutaneous adipose tissue samples. While beyond the scope of this current proposal, this biorepository will allow for future studies to better understand the mechanisms by which HIIT and/or bariatric surgery improve DSP outcomes. Which intervention to pursue will be based on which intervention(s) is/are successful at improving DSP outcomes in this clinical trial. Drs. [name] (co-I, HIIT) and [name] (consultant, bariatric surgery) have the expertise to explore mechanisms in humans. As Director of the Obese-Adipose Tissue Research Laboratory, [name] will help obtain and process the subcutaneous adipose tissue obtained for this proposal. [name] (consultant, murine DSP outcomes), in conjunction with Drs. [name] and [name] (consultants, murine bariatric surgery), has the expertise to explore mechanisms in mice. The biorepository will allow translational research from mouse to human and from human to mouse. Our experienced team of investigators and consultants is uniquely positioned to accomplish this goal.

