C3.2.1 HIIT: Training sessions during the 24-mo will be supervised by exercise physiologists and trainers. [name], the director of the Human Phenotyping Core (HPC) of the U-M's Nutrition and Obesity Research Center will provide oversight of this aspect of the study given his vast expertise on the impact of HIIT and other exercise interventions on metabolic outcomes.⁴⁶⁻⁵⁰ The exercise modality will be self-selected (e.g., walk/run (outdoors or treadmill), elliptical machine, stair climbing, cycling), and subjects will be encouraged to regularly vary the exercise modality to reduce risk of overuse injury and to enhance the variety of the exercise program.

Subjects receiving the surgery intervention will start the HIIT regimen no sooner than 4 wk post-operatively to provide an adequate time to heal from the procedure. All subjects will first undergo a familiarization program for 1 week where they all will perform conventional exercise (steady-state at 65% HR max for 25 min/session). After this 1-week familiarization period, subjects will begin the HIIT regimen. The first session of the "ramp-up" period will entail 19 min of conventional exercise at 65% HR max, followed immediately by 2 x 1 min intervals at 90% HR max with a 1 min active recovery period between intervals at 50% HR max, and a 3 min cool down at 60% HR max after the second interval. After that first ramp up training session, 1 additional high intensity interval will be added to each training session, so by the beginning of week 3 of HIIT training, subjects will reach the full HIIT training protocol of a total of 10 x 1 min intervals at 90% HR max (**Figure 2**). They will continue this training protocol, 3 sessions/wk (2 supervised and 1 unsupervised), for 24-mo. Subjects who may feel challenged by the rate of increase in the number of intervals during this ramp up period will be allowed to increase the number of intervals at a slower pace, but all subjects must reach the full HIIT protocol during week 4 of HIIT training. Of note, our team regularly has patients with obesity and/or diabetes progress to the full protocol HIIT within 3 weeks, demonstrating the feasibility of this training approach in our population. 38, 41, 62, 63

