Skin biopsy is a minimally invasive procedure, with less than 1% reporting mild adverse events such as bleeding, swelling, or erythema. It allows morphometric quantification of C-fibers in the epidermis (IENFD).77,78 Data from several clinical trials show that decreased IENFD is a robust measure of the clinical signs and symptoms of DSP^{77, 79-86} and correlates with a patient's perception of neuropathic pain.^{77, 78} Serial measurements of IENFD may be performed to assess the therapeutic efficacy of drugs^{77, 78, 87, 88} and/or lifestyle interventions³⁰ in arresting disease progression and providing pain relief, and a large normative database was recently created by an international consortium.^{77, 78, 89} Published guidelines concur that IENFD is the standard for the diagnosis of small fiber sensory neuropathy. 77, 87, 90, 91 Further support for IENFD as an early biomarker is the observation of reduced density in patients with pre-diabetes compared to those with normal glucose tolerance. 30, 83 Finally, several studies report increased IENFD in response to the rapeutic interventions that correlate with improvements in the signs and symptoms of DSP. 83-85 IENFD is also endorsed by several societies and authorities in the field as diagnostically efficient at distinguishing patients with early small fiber neuropathy from normal controls, and as a reliable and valid outcome measure to assess DSP in clinical trials. 77, 79, 87, 90, 92 In summary, IENFD is a sensitive and reliable measure of early DSP, its loss directly correlates with increasing DSP severity, is amenable to improvement with appropriate intervention, is safe and easy to perform, and to date represents the gold-standard method for evaluating morphological changes in small nerve fibers. 77, 79, 87, 90, 91 In addition, the PI has used this procedure extensively in two ongoing studies with excellent patient compliance (NS-079417 and 2P30-DK020572). Thus, IENFD was selected as the most appropriate and informative primary endpoint in the current clinical trial.

- **C3.4.2 Secondary outcomes:** Selecting the most appropriate outcome measures is critical in the design of an interventional clinical trial and essential to obtaining clinically relevant information on the true response to the intervention. Thus, we will evaluate changes from baseline to 3, 12, and 24 months in several secondary outcomes:

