- b) Questionnaires that ask about the participant's mood and how weight has impacted participant's physical and emotional health. These questionnaires include the EQ-5D, IWQOL-Lite, Godin Leisure-Time Exercise, and a brief physical activity questionnaire.
- c) Demographic questionnaire will be administered to participants.

8. Functional scales:

- a) The Berg Balance Scale, measures balance in 14 separate activities of daily living (the unipedal stance portion has been shown to be particularly reflective of DSP-related mobility loss)¹¹⁰:
- b) The 8 Foot Up and Go Test, a test of functional mobility that assesses the time needed for a subject to arise from sitting position, walk 8 ft and turn 180 degrees around a cone, and return to sitting¹¹¹;
- c) The Modified Falls Efficacy Scale, assessing patient's self-reported ability to perform activities of daily living (e.g. get dressed/ undressed, walking, shopping)^{86, 112, 113} The fall survey will also ask "Have you fallen within the last year? If yes, how many falls?"

9. Qualitative sensory testing:

a) Neurothesiometer- quantitative measure of vibration threshold at both toes.

10. Cognitive impairment:

- a) NIH Toolbox Cognitive Battery A 30-minute brief computerized battery comprised of tasks covering several cognitive domains including language, attention, working memory, episodic memory, executive function, and processing speed. The NIH Toolbox Cognitive Battery is a reliable and valid instrument of cognitive function⁴⁸.
- b) The Rey Auditory Verbal Learning Test will be presented in addition to the NIH Toolbox. The Rey is presented verbally to the participant and is important as a supplement to the single visual-based short memory task in the NIH Toolbox. The computer format and national standardization of this tool will allow for comparisons to future studies. We will partner with [name] who has expertise in these cognitive assessments.
- 11. *Urine*: Urine albumin/creatinine ratio and serum creatinine measurements. Urine samples will be stored in the biorepository.
- 12. Anthropometric measurements: Body measurements at different site circumferences will be measured at each study visit including: abdomen, arm, buttocks/hips, calf, forearm, hips/thigh, mid-thigh and waist.
- 13. Orthostatic Hypotension: Blood pressure and heart rate will be assessed after patient is supine for 5 minutes, standing for 1 minute and at 3 minutes standing.

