| Anthropometric measures^ | | X | X | X | X |
| Orthostatic Hypotension Assessment [^] | | Х | X | X | Х |
| Quality of Life measures: | | | | | |
| NeuroQol | | X | X | X | X |
| Questionnaires | | X | Х | Х | X |
| Demographics | | X | | | |
| Functional Assessments | | | , . | , . | |
| Berg Balance Scale [^] | | X | X | X | X |
| 8-foot Get Up and Go Test^ | | X | X | X | X |
| Modified Falls Efficacy Scale | | Х | X | Х | Х |
| Aerobic Assessment | | | | | |
| VO2 max | X | | | | X ⁺ |
| | | | | | |
| Dual Energy X-ray Absorptiometry | | | | | |
| Duai Lineigy A-iay Absorptionietry | | X | | | X |

^{*}Randomization to exercise protocol to occur after baseline visit

Data collected for clinical purposes as part of the Adult Bariatric Surgery Program will be reviewed as part of this study and included in the study records.

- **C3.6. Timeline and milestones:** The planned study duration is 5 yr, with 2 yr of subject accrual, 2 yr of subject follow-up, plus 1 yr for analysis and results presentation.
- **C3.7. Statistical analysis:** The four treatment groups (HIIT/no surgery, HIIT/surgery, routine exercise/no surgery, routine exercise/surgery) will be compared with respect to demographic and baseline variables (e.g., age, sex, glycemic status, OGIS, BMI, etc.). If a significant difference is found in any variable, the models described below will be fitted after adjusting for these variables.
- C3.7.1 Analysis of primary outcome: The primary outcome is IENFD at the proximal thigh, measured at baseline, 3, 12, and 24 mo. Exploratory analysis will be performed to assess the need for any transformation

^{*}Only participants randomized to the HIIT will complete a second time

 $^{^{\}mathsf{T}}$ Participants can consent to have skin biopsy added to biorepository

[^]Participants may complete the consent and outcomes virtually prior to the upcoming visit to decrease in-person interaction due to Covid-19. If the outcome cannot be completed successfully it with be completed during the visit.

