
C3.7.2 Analyses of secondary outcomes: Due to the pitfalls of multiple testing, formal statistical testing won't be performed. For analysis of repeated measures of continuous data (CCM, cardiovascular reflex tests, MNSI, UENS, mTNS, SAS, McGill Pain questionnaire, NeuroQOL, and functional assessments), the longitudinal approaches described above will be employed. Specifically, each outcome will be analyzed separately using a linear mixed effect regression model, with the treatment group as the primary exposure.

C3.7.3 Exploratory analyses: To investigate the potential modifying effects of sex, we will perform an additional analysis that includes an interaction term between the intervention groups and sex. Similarly, we will explore the differential effect of sleeve gastrectomy versus Rou-en-Y gastric bypass by including separate indicator variables for these two different surgical techniques. We will also investigate the potential weight loss independent effects of bariatric surgery by evaluating the earliest time point (3 months). In addition to other metabolic syndrome components, we will study the effect of change in insulin sensitivity as measured by OGIS on our primary outcome. Finally, we will perform an analysis of those who complete more than 80% of supervised exercise sessions to assess the effect of exercise compliance. Importantly, these analyses will be hypothesis generating for future studies.

C3.8. Power calculation: The purpose of this clinical trial is to provide the preliminary data necessary to design a multicenter clinical intervention trial. Therefore, it is not strictly amenable to formal power

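### The one-year fall question is also asked at Month 3, where about three quarters of its recall precedes Day 0, so any effect on falls is diluted about four-fold at that visit

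*Protocol*

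**What the plan says.** Protocol C3.4.2, functional scales, item 8c names the Modified Falls Efficacy Scale and attaches a further item to it: "The fall survey will also ask" the participant "Have you fallen within the last year? If yes, how many falls". This is the only wording given. It asks for a yes/no and a count, not for dates.

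Table 6 (C3.5) has a row for the "Modified Falls Efficacy Scale", marked at baseline and at Months 3, 12 and 24. The fall question has no row of its own and no visit-specific version. Each follow-up visit has a window of ±14 days; baseline may take place from Day -70 to Day 0. A footnote adds: "Randomization to exercise protocol to occur after baseline visit".

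On use, C3.4.2 states that "we will evaluate changes from baseline to 3, 12, and 24 months in several secondary outcomes". C3.7.2 covers repeated continuous measures, and its list ends with "NeuroQOL, and functional assessments), the longitudinal approaches described above will be employed". The same section rules out formal tests of secondary outcomes.

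**The concern.** A follow-up question should cover time in which the intervention could have acted. Here a participant seen three months into the trial is asked about a whole year, most of which came before the trial treatment. The baseline visit has already asked about much of that same period. Because no dates are recorded, no later analysis plan can separate falls before Day 0 from falls after it. This is a matter of what the form collects, not something that can be left to the statistical analysis plan.

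Two comparisons are affected differently. Between the randomised HIIT and counseling arms, earlier falls should balance on average, so the difference shrinks towards zero. Between surgery and no surgery, which is not randomised, earlier falls need not balance, and a raw Month 3 difference would consist mostly of history in self-selected groups.

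The protocol lists falls among the harms of DSP in its aims and in A1, and C3.7.3 gives the three-month visit a purpose of its own as the earliest look at surgery. A near-null fall result at Month 3 could be misread as evidence of no early effect.

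**Working it through.** The protocol states no fall rate, sample size or power for falls, so there is no planned figure to reproduce.

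**Inputs from the protocol.** Recall of 12 months (item 8c); Month 3, 12 and 24 visits, each ±14 days, and baseline from Day -70 to 0 (Table 6). For the timing of HIIT, C3.2.1 says: "Subjects receiving the surgery intervention will start the HIIT regimen no sooner than 4 wk post-operatively" and "All subjects will first undergo a familiarization program for 1 week".

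**Assumptions.** Day 0 is the start of the intervention period from which the follow-up months are counted. The fall rate is constant apart from the treatment effect, and the effect starts at Day 0.

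**Step 1: share of the recall before Day 0.** Share = (365.25 − days from Day 0 to the visit) / 365.25, and zero if negative.

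| Visit | Early (−14 d) | Nominal | Late (+14 d) |
|---|---|---|---|
| Month 3 (day 91.3) | 79% | 75% | 71% |
| Month 12 | 4% | 0% | 0% |
| Month 24 | 0% | 0% | 0% |

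**Step 2: share before HIIT itself, nominal Month 3 visit.**
- HIIT after a 1-week familiarization from Day 0: 1 − (91.3 − 7)/365.25 = 77%.
- HIIT 4 to 5 weeks after Day 0, if Day 0 is the surgery date (assumption): 1 − (91.3 − 28)/365.25 = 83% to 1 − (91.3 − 35)/365.25 = 85%. With an early visit and 5 weeks it is 88%.

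**Step 3: dilution.** With 25% of the recall after Day 0, observed rate ratio = 0.75 + 0.25 × true rate ratio.
- True 0.5: 0.75 + 0.125 = 0.875.
- True 0.3: 0.75 + 0.075 = 0.825.
- Falls abolished entirely: 0.75.

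One quarter of the absolute difference in rate remains, hence four-fold.

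**Step 4: overlap with baseline.** The Month 3 recall runs from about Day -274 to Day 91. If baseline is on Day 0, about 274 days (9 months) are asked about at both visits. If baseline is on Day -70, the overlap is 274 − 70 = 204 days (6.7 months).

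**Step 5: illustrative power.** Assumed: 60 HIIT versus 60 counseling (two groups of 30 each, from C3.8), 0.3 to 1.0 falls per person-year, Poisson counts, true rate ratio 0.5, two-sided alpha 0.05. Power = Φ(|ln ratio| / SE − 1.96), with SE = √(1/expected falls in one arm + 1/expected falls in the other).
- One-year recall, 0.5 falls per year: 30 versus 26.25 falls, SE = 0.267, |ln 0.875| = 0.134, power 7%.
- Recall since Day 0, same rate: 7.5 versus 3.75 falls, SE = 0.632, |ln 0.5| = 0.693, power 19%.
- Over 0.3 / 0.5 / 1.0 falls per year: 6% / 7% / 11% with the one-year recall, and 13% / 19% / 34% with recall since Day 0.

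These figures show relative information only, since no test of falls is planned.

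**The case against.** The strongest reply is that this is a small matter. The named outcome in 8c is the scale, which rates self-reported ability and has no one-year recall. The fall question is an add-on, and no fall-rate endpoint is defined. C3.7.2 speaks of continuous data, so it is not certain that a yes/no answer and a count enter the mixed model. No secondary outcome is formally tested. For choosing phase 3 secondary outcomes, C6 names IENFD, CCM and NCS, not falls. All of this stands and limits the weight of the point.

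A reader might infer that the Month 3 answer cannot show a treatment effect at all. The arithmetic does not support that: a true ratio of 0.5 reads 0.875, not 1, and earlier falls balance on average between the randomised arms.

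A reader might also infer that falls are double-counted. The recall periods do overlap: baseline with Month 3, and Month 3 with Month 12 for the first three months. But no total over visits is planned, so no stated analysis counts an event twice. The overlap only makes repeated answers more alike.

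Finally, one may say that the change from baseline takes care of earlier falls. It does so only in part. With perfect recall and baseline on Day 0, the Month 3 change equals falls in the first three months minus falls in the oldest three months of the baseline year. An earlier baseline or faulty recall breaks even that.

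**Conclusion.** The point holds in limited form. As written, the protocol asks a one-year question at a three-month visit. About 75% of the recall (71% to 79% across the visit window) precedes Day 0, and the share before HIIT is larger in surgical patients if Day 0 is the surgery date. Under a constant fall rate, any effect on falls is diluted about four-fold, so the Month 3 fall answer tells little about HIIT and, for surgery, mostly describes pre-treatment history.

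The defect is confined to the yes/no and count item at Month 3. The Modified Falls Efficacy Scale score, the Month 24 fall data and the primary outcome are not affected; Month 12 is affected by at most about 4%, and only with an early visit. The shares follow from the protocol's own schedule, given the reading of Day 0 stated above. The rate ratios and power figures rest on assumed fall rates and effects. The change is worth making because the information lost at Month 3 cannot be recovered afterwards, although little in the trial's stated conclusions depends on it.

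**What to change.** - **Month 3 only:** ask whether, and how often, the participant has fallen since Day 0, with the calendar date of Day 0 on the form. Express the count as a rate per person-time, because the visit window varies. Do not anchor to the previous visit: with baseline on Day -70, that span would be 70 + 91 = 161 days, of which 70 (43%) still precede Day 0.
- **Baseline, Month 12 and Month 24:** keep the one-year question. These windows match each other and the follow-up ones lie essentially after Day 0.
- **Month 3 answers already collected with the one-year wording:** leave them out of the treatment comparison of falls.

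This costs one reworded item on one form and one sentence on analysis, with no extra visit or procedure. There are two drawbacks. The Month 3 yes/no answer will no longer be directly comparable with the 12-month baseline answer, and a three-month window yields few falls (illustrative power 13% to 34% under the assumptions above). The Month 3 result will be imprecise, but no longer diluted by falls before Day 0.

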those that do not have surgery. We will also stratify by glycemic status to limit confounding. Randomization will be performed using permuted blocks, with a block size known only to the statistician. We will perform longitudinal analyses using linear mixed models to study the evolution of IENFD from baseline to 2 yr (4 measures in total). We will compare the effect of HIIT, bariatric surgery, and the combination of HIIT and surgery on all outcomes.

C1. Aim 1: Examine the efficacy of a HIIT exercise regimen on DSP outcomes (randomized)

C1.1. Introduction: There is an urgent need for a disease modifying therapy for the prevention and treatment of DSP. Currently, physicians only have neuropathic pain medications and glucose control to offer patients with DSP.^{7, 27} However, glucose control alone is not effective at preventing DSP and many patients with diabetes develop DSP despite good glucose control.²⁷ Similarly, no disease modifying interventions exist for the increasing population with pre-diabetes and/or obesity. Thus, it is essential to identify new interventions that can prevent and treat DSP. To date, uncontrolled studies support improvement in the natural history of DSP decline over time after an exercise intervention.²⁸⁻³⁰ The next step is to determine whether a randomized, intensive, exercise intervention improves DSP outcomes compared to routine exercise counseling.

C1.2. Justification & feasibility:

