- C3.2.3 Bariatric surgery: Patients will undergo the surgical procedure as recommended by their surgeon as part of their routine care at a bariatric clinic. Our preliminary data indicates that 85% of patients had a sleeve gastrectomy, 15% had a Rou-en-Y gastric bypass at the University of Michigan, and none had an adjustable gastric band. We expect a similar distribution of procedures as part of this proposed study. Patients undergoing sleeve gastrectomy and Roux-en-Y gastric bypass have similar weight loss and time to stabilization, which limits potential confounding by type of surgical procedure. ^{59, 60} Specifically, weight loss is typically 60-80 pounds at 6 mo, and 100-120 pounds at one year with stabilization at 1-1.5 yr. In contrast, adjustable gastric band procedures result in a 45-55 pound weight loss at 6 mo with stabilization at 2 yr, but this procedure is not performed at U-M. Of note, as part of their routine post-operative care, patients are supplemented with a multivitamin, sublingual B12, and calcium. Furthermore, patients have laboratory monitoring including comprehensive metabolic panel, complete blood count, B12, TSH, ferritin, and vitamin D. The prophylactic supplementation and laboratory monitoring mitigate the potential for nutritional deficiencies to lead to nerve injury and subsequent DSP. The strength of this approach is that it mirrors current practice in the bariatric surgery, a specific nutritional deficiency other than B12 deficiency is often not found. ⁶⁸
- **C3.3. Metabolic phenotyping:** These tests will aid in the appropriate description of the population, allow for adjustment of potential confounding as needed, and may provide further data in support of the metabolic factors that improve when IENFD increases over time.

Phenotypic tests will occur at baseline, 3, 12, and 24 mo, with the exception of the GTT which will only be performed at baseline. The metabolic phenotyping tests include:

 2 hr, 75 gram oral GTT with glucose and insulin levels drawn at 0, 30, 60, 90, and 120 min to allow categorization of glycemic status as well as calculation of Oral Glucose Insulin Sensitivity (OGIS).
Participants with a known diagnosis of diabetes will not complete an OGTT. Participants with a fasting glucose >126 mg/dL will not complete the test. Fasting glucose and insulin levels will be drawn at the 3, 12 and 24 month time points;

- 2. Hemoglobin A1C;

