on the primary outcome variable. The primary exposure variables are HIIT: yes/no (Aim 1), and bariatric surgery: yes/no (Aim 2). We will adjust for demographic, clinical, and baseline characteristics as covariates in the model. In addition to the main effects of HIIT exercise program and bariatric surgery, we will also examine selected interactions based on *a priori* considerations. In particular, we will focus on the interaction between HIIT and bariatric surgery to assess if the effect of HIIT exercise on IENFD is modified by bariatric surgery. Linear mixed effects regression modeling will be used to determine the relationship between the primary exposure variables and IENFD over time. Longitudinal data analysis approaches such as this offer enhanced statistical power, as subjects are able to serve as their own reference. Furthermore, linear mixed effects regression offers a flexible framework to handle missing data such as due to attrition. Let Y_{it} denote the IENFD of the *i*th patient at the *t*th time point. Then Y_{it} can be modeled using the random intercept model.¹¹⁴ The random intercept model can be viewed as arising from a two-stage model as follows:

Stage 1: subject-specific trajectory: $Y_{it} = \mu_{0i} + \lambda' Z_i + \underline{\theta' X}_{it} + \underline{e}_{it}$

Stage 2: between-subjects: $\mu_{0i} = \beta_{00} + \beta_{0i}$

Combining the two stages, we can write $Y_{it} = \beta_{00} + \beta_{0i} + \theta' X_{it} + e_{it}$

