where β_{00} is the population-averaged intercept, Z_i is the matrix of main effects and interaction corresponding to HIIT exercise and bariatric surgery, \underline{X}_{it} is the matrix of fixed covariates (demographic and baseline characteristics), λ and θ are the vectors of corresponding fixed effects parameters, β_{0i} is the subject-specific random (intercept) effect capturing heterogeneity across subjects due to unmeasured confounders, and en is the random error characterizing variation due to sources like within-subject fluctuations and measurement error. The random effect β_{0i} is assumed to follow a normal distribution with mean zero and variance σ^2_{sub} , and the eit's are assumed to be distributed normally with mean **0** and variance covariance matrix R (non-diagonal). Furthermore, we also assume that θ_{0i} and e_{it} are independent. Maximum likelihood method will be used to estimate the model parameters. We will use Akaike Information Criterion (AIC) and Schwarz Bayesian Information Criterion (BIC) to guide the selection of the covariance structure. Inference for λ (which is of primary interest) will be based on Wald tests. We will use PROC MIXED in SAS to fit the above model. To explore potential non-linear or threshold effect of treatment exposure on IENFD we will use a nonparametric regression model fitted using the framework of generalized additive models (GAM). 115 Given the exploratory nature of the research proposed here, the GAM models will allow us the flexibility to include a smooth functional term instead of restricting to a linear relationship. The smoothing term is fitted by using penalized regression splines or locally smoothed loess curves, with the degree of smoothness chosen in a data-adaptive way, using cross-validation techniques. We will use the gam function in the mgcv package available in the R software to fit these non-parametric regression models. We will perform sensitivity analyses to assess how subjects who withdrew affect conclusions of the analysis. An intent-to-treat analysis set (including subjects who are randomized, treated, and have a baseline IENFD) will be used to assess treatment effects, with multiple imputation methods¹¹⁶ employed to impute outcomes for subjects with missing post-baseline data. Depending on the extent and pattern of missingness, other simpler sensitivity analyses may be used: e.g., subjects completing the study (completers) may be analyzed using a repeated measures analysis of variance model. The model will include the same covariates that are included in the primary analysis.

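### Protocol C3.7 lets significance tests of baseline differences decide covariate adjustment, does not fit with the unconditional adjustment in C3.7.1, and is a poor rule whichever way the two are read together

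*Protocol*

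**What the plan says.** Section C3.7 compares the four groups (HIIT or routine exercise, with or without surgery) on an open-ended list of baseline variables that names age, sex, glycemic status, OGIS and BMI. It then gives a rule: "If a significant difference is found in any variable, the models described below will be fitted after adjusting for these variables". It names neither the test nor the significance level.

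Section C3.7.1, which describes the first of the models meant, has no such condition: "We will adjust for demographic, clinical, and baseline characteristics as covariates in the model". The model equation there carries these covariates as a fixed term. The completers' sensitivity analysis inherits the set: "The model will include the same covariates that are included in the primary analysis".

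Section C3.3 says of the metabolic tests that they will "allow for adjustment of potential confounding as needed". Section C says of the randomization: "We will also stratify by glycemic status to limit confounding". Aim 1 (HIIT) is labelled randomized; Aim 2 (surgery) is labelled non-randomized and exploratory.

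**The concern.** Two analysts could fit different primary models from this text. One would read C3.7 as choosing which of the C3.7.1 covariates enter; the other would read it as adding further variables to them. The completers' analysis would follow whichever model was fitted.

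Under either reading, a baseline p-value helps to decide the model, and it answers the wrong question for both aims. For HIIT, differences between randomized arms are chance, and a covariate earns its place by predicting the outcome. For surgery, real differences are to be expected. A confounder biases the contrast in proportion to its imbalance and its link to the outcome, not according to whether a test with 35 patients per group detects it.

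At stake are precision for Aim 1, possible residual confounding for Aim 2, and a covariate set that is settled only after the baseline data have been seen.

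**Working it through.** The plan gives no figure to reproduce here, so the check is of how the rule behaves.

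**Inputs from the protocol.** 35 patients per group, 140 in all (C3.1); four groups compared (C3.7); surgery not randomized (Aim 2).

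**Assumptions.** Screen at the two-sided 5% level; true surgery imbalance in one covariate of s = 0.3, 0.4 or 0.5 SD; correlation r = 0.3 or 0.5 between the covariate and a single subject-level outcome of SD 1; no true treatment effects.

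**Step 1: how often the screen flags a real surgery imbalance.** C3.7 names no test, so two are shown.

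- Four-group omnibus F test: group means (0, s, 0, s), noncentrality 140 × (s/2)², on 3 and 136 degrees of freedom. For s = 0.4 this is 140 × 0.04 = 5.6.
- Direct comparison of 70 surgery with 70 non-surgery patients: t test, noncentrality s × √(70/2). For s = 0.4 this is 0.4 × 5.916 = 2.37.

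| True imbalance | Omnibus test flags | Direct test flags |
|---|---|---|
| 0.3 SD | 28% | 42% |
| 0.4 SD | 48% | 65% |
| 0.5 SD | 68% | 84% |

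At the 30 per group expected after attrition (C3.8), the omnibus rates are 24%, 41% and 61%.

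**Step 2: effect on the surgery contrast if the screen selects covariates.** Simulation of 20,000 trials of 140 patients. The model has surgery and HIIT main effects, with the covariate added only when flagged.

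| Rule | Surgery bias (SD units) | Surgery type I error |
|---|---|---|
| No adjustment | 0.09 to 0.25 | 8 to 31% |
| Omnibus screen | 0.03 to 0.08 | about 6 to 9% |
| Direct screen | 0.01 to 0.06 | about 5.5 to 7% (down to 5.3% in a repeat run) |
| Always adjust | 0.00 | 5% |

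For the omnibus screen, the bias at s = 0.3, 0.4 and 0.5 is 0.051, 0.045 and 0.033 with r = 0.3, and 0.084, 0.075 and 0.053 with r = 0.5. It falls as the imbalance grows because larger imbalances are flagged more often.

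**Step 3: effect on the HIIT contrast.** There is no bias, and type I error under the omnibus screen is 4.6 to 5.0%. In theory, always adjusting multiplies the standard error by about √(1 − r²): 0.954 for r = 0.3 and 0.866 for r = 0.5. Simulated standard errors with no surgery imbalance agree:

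| r | No adjustment | Omnibus screen | Always adjust |
|---|---|---|---|
| 0.3 | 0.169 | 0.168 | 0.162 |
| 0.5 | 0.170 | 0.167 | 0.148 |

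Fixed adjustment therefore gains about 4% (1 − 0.162/0.169) or 13% (1 − 0.148/0.170). The omnibus screen gains about 1% or 2%, and a direct surgery test less still, so 0 to 2% across the two.

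**The case against.** The reading that contradicts neither sentence is that C3.7 adds to the C3.7.1 set. Variables already in that set are then safe, glycemic status among them as a baseline characteristic, and the bias in Step 2 does not arise for them. This stands: every bias and type I figure for surgery is conditional on the other reading. The additive reading does not rescue the rule, though, because variables outside the set would still enter or stay out by p-value.

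The flag rates also depend on the test. The direct comparison detects more and leaves less bias, which is why both are shown. The rule is stated in advance and looks only at baseline data, so follow-up results cannot steer it. Aim 2 is exploratory. The lack of a closed covariate list may properly be left to a statistical analysis plan. The C3.3 phrase explains why tests are collected and is weak evidence of an analysis rule. All of this limits the size of the point. What remains is that the protocol itself states a significance trigger and does not reconcile it with C3.7.1.

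Three stronger inferences are tempting, and the documents do not support them:

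- That the primary HIIT result is biased or its type I error inflated. Randomization protects it, and Step 3 shows neither.
- That the surgery bias can be expressed in fibers/mm using the SD of 7.0 and the expected differences in C3.8. Those describe two-year change, whereas the treatment effect in the C3.7.1 equation has no time term, and Step 2 uses a single outcome per patient. The conversion would mix two estimands.
- That covariate-by-time terms are needed to cure this fault. C3.7.1 does aim to "determine the relationship between the primary exposure variables and IENFD over time", but such terms become relevant only if the target is a group-by-time contrast. That is a separate matter from the significance trigger.

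**Conclusion.** The concern holds, at moderate size. C3.7 states a significance-triggered adjustment rule, C3.7.1 states unconditional adjustment, and the protocol does not say how they fit together. The final covariate set depends on baseline p-values under either reading.

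For Aim 1 the cost is precision only, and its size rests on the assumed correlations. For Aim 2 there is modest residual confounding, only if the screen selects covariates; its size rests further on the assumed 5% level, the test used, the imbalance, and the single-outcome simplification. If the screen merely adds variables, the harm for those already covered is nil, and what remains is the data-dependent model. The trial's primary conclusion is not invalidated, but the rule has no advantage over a list fixed in advance.

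**What to change.** Delete the significance trigger from C3.7 and make the section agree with C3.7.1: fit the models with a covariate list fixed in advance, whatever the baseline p-values. Always include glycemic status, since the randomization is stratified by it. Add a few prognostic variables or likely surgery confounders chosen on subject-matter grounds, for example age, sex and one obesity measure. Keep the four-group baseline comparison as description.

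The cost is a change of wording and no new data, since the example variables are already collected at baseline. As main effects the example list uses about 5 degrees of freedom among 140 patients: glycemic status 2, age 1, sex 1, obesity measure 1.
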